A Bayesian analysis for the primary endpoint will be performed using an analysis of covariance (ANCOVA). The ANCOVA model for the change from baseline in the monthly number of migraine headache days will include terms for treatment and type of migraine, and baseline number of migraine headache days as a covariate will be used.

Frequentist analyses for change from baseline in the monthly number of migraine headache days and change from baseline in the monthly number of headache days will be performed using the same ANCOVA model.

Comparisons between the treatments in rate of responders will be conducted using Cochran Mantel Haenszel tests that are stratified by the type of migraine.

For continuous variables, descriptive statistics will include the number of patients, mean, median, standard deviation, minimum, and maximum. Categorical variables will be summarized using the number and percentage of patients.

2. Schedule of Activities

Table LAJB 2.1 Schedule of Activities

	Screening	Baseline	Treatment Phase			Follow-up						ED ^b
(Target) Interval (days) since previous visit	-	-	30	15	15	15	15	15	15	30	30	
Allowable range (days) between visits	3-90	30-40 ^a										
Interval allowance (days)			+5	±3	±3	±3	±3	±3	±3	±3	±3	
Visit	1	2	3	4	5	6	7	8	9	10	11	
Month	-	-	0	.5	1	1.5	2	2.5	3	4	5	
Informed consent	X											
Demographics	X											
Physical examination ^c	X	X	P	X	X	X	X	X	X	X	X	
Neurological examination	X	X	P	X	X		X		X	X	X	
Height ^d and weight	X		P								X	X
Medical history ^e and concurrent conditions	X											
Vital signs ^f	X		P, 1 h	X	X	X	X	X	X	X	X	
12-lead ECG ^g	X	X	P	X	X		X		X		X	X
Serum pregnancy test (WOCBP only) or FSH	X											
Urine pregnancy test (WOCBP only) ^h		X	P		X		X		X	X	X	X
HIV, hepatitis B and C	X											
Hematology, chemistry ⁱ (include eGFR)	X	X	P	X	X	X	X	X	X	X	X	
Creatine kinase (Total CK)	X		P	X	X		X				X	X
HbA1c			P		X							
Urinalysis	X	X	P		X		X					
CCI			P	X	X							
ePRO and headache medication log training		X										
Inclusion and exclusion criteria	X	X	P									
ePRO daily patient diary entry		X	X	X	X	X	X	X	X	X		
Headache medication log		X	X	X	X	X	X	X	X	X		
CCI		X	X	X	X	X	X	X	X	X		
CCI		X	X	X	X	X	X	X	X	X		
Randomization			P									
Study drug administration			X									
MSQ v2.1			X		X		X		X		X	
HIT-6			X		X		X		X		X	

	Screening	Baseline	Treatment Phase			Follow-up						ED ^b
(Target) Interval (days) since previous visit	-	-	30	15	15	15	15	15	15	30	30	

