5.1. Overall Design

Study LAJB is a multicenter, randomized, double-blind, parallel, placebo-controlled study of LY3451838 in patients who meet the International Classification of Headache Disorders version 3 (ICHD-3) criteria for a diagnosis of migraine with or without aura, or chronic migraine, and who have previously failed 2 to 4 categories of standard-of-care treatments for migraine prevention. The study has 4 periods as described below.

Figure LAJB 5.1 illustrates the study design.

Study Period I (Screening): The study and potential risks will be explained to the patient at Visit 1. The informed consent form (ICF) must be signed before any study procedures are performed, which includes discontinuing excluded medications. Patients are required to discontinue all excluded medications or treatments for migraine prevention at least 2 weeks prior to Visit 2. Botulinum toxin A or B in the head or neck area for therapeutic use must be discontinued at least 3 months prior to Visit 2. Nerve blocks or device use, such as transcranial magnetic stimulation, in the head or neck area for migraine prevention are not allowed within 30 days before Visit 2.

The screening visit (Visit 1) will consist of a full clinical assessment (see Schedule of Activities, Section 2). Visit 1 will be complete when the last scheduled procedure of the screening assessment for the patient is completed.

Study Period II (Baseline): Qualified patients will enter Study Period II (prospective baseline) to determine their eligibility for the study and to establish baseline data for comparison of endpoints during the treatment phase. Beginning at Visit 2, patients will log in daily to the electronic patient-reported outcomes (ePRO) system to answer questions about the occurrence of headaches, headache duration, headache features, severity of headache, and whether any acute headache medication was taken. At Visit 2 and if available, patients will receive the devices required for digital biomarkers assessments as well as the necessary instructions and training. Also beginning at Visit 2, patients will record the name, dose, and date of any acute headache medication on a headache medication log which will be returned to site staff at each study visit. At the end of the prospective baseline period, sites will be notified whether their patient met criteria and are eligible to be randomized at Visit 3.

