5.5. Justification for Dose

The planned LY3451838 dose for this study is CCI IV CCI for a 60-kg individual). This dose is selected based on the available preclinical pharmacology, toxicology, and clinical data.

Based on the CCI model, the predicted therapeutic concentration of LY3451838 is approximately CCI. In Study LAJA the observed plasma concentration of LY3451838 28 days after a single IV dose of CCI This dose is chosen to ensure adequate target engagement that enables testing the efficacy of LY3451838 for migraine prevention, and to account for uncertainty in the translation of preclinical model to human efficacy.

The CCI dose was the highest dose administered in the single ascending dose study, LAJA. Interim analysis of the ongoing LAJA study suggested that LY3451838 was well-tolerated after a single IV dose up to CCI. No dose-limiting toxicity was identified in this study, and no evidence of immune complex disease or vasculitis was observed. Vital signs and safety

laboratory tests were also unremarkable. The available safety / tolerability data from the ongoing study LAJA support the administration of [REDACTED] CCI [REDACTED] single IV dose in Study LAJB.

This dose is also supported by the available toxicology data. [REDACTED] CCI [REDACTED]

[REDACTED] summarized in IB Section 4.2). [REDACTED] CCI [REDACTED]

Based on the available toxicology and limited clinical data, this dose is acceptable in this single-dose efficacy study.

6. Study Population

Prospective approval of protocol deviations to recruitment and enrollment criteria, also known as protocol waivers or exemptions, are not permitted.

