6.2. Exclusion Criteria

Patients will be excluded from study enrollment if they meet any of the following criteria at Visit 1, unless stated otherwise in respective criterion:

19. Are currently enrolled in any other clinical study involving an investigational product or any other type of medical research judged not to be scientifically or medically compatible with this study.
20. Have participated, within the last 30 days or 5-half-lives (whichever is longer), in a clinical study involving any investigational product. If the half-life of the investigational product is unknown, 6 months should have passed prior to Visit 1.
21. Have previously completed or withdrawn from this study or any other study investigating LY3451838.
22. Known hypersensitivity or intolerance to monoclonal antibodies or other therapeutic proteins, or to common antihistamines, epinephrine, methylprednisolone or other systemic corticosteroids.
23. Are currently receiving medication or other treatment for prevention of migraine headaches. Patients must have discontinued such medications or treatments at least 2 weeks prior to Visit 2. Botulinum toxin A and B that has been administered in the head or neck area use must be discontinued at least 3 months prior to Visit 2. Nerve blocks or device use (such as transcranial magnetic stimulation or electrical nerve stimulation) in the head or neck area for migraine treatment must be discontinued at least 30 days prior to Visit 2. Anti-CGRP antibodies (to either ligand or receptor) must be discontinued at least 5 half-lives prior to Visit 2.
24. Have previously failed more than 4 migraine preventive medication categories in the past 10 years from the medication list in Inclusion Criterion # 6 due to inadequate efficacy (that is, maximum tolerated dose for at least 2 months) and/or safety/tolerability reasons. Previous failures to medications not on the above list will not be considered toward this exclusion.

25. History of cluster headache or migraine subtypes including hemiplegic (sporadic or familial) migraine, ophthalmoplegic migraine, retinal migraine, typical aura without headache, complications of migraine and migraine with brainstem aura (basilar-type migraine) defined by IHS ICHD-3.

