7.8. Concomitant Therapy

Table [LAJB 7.1](#) contains the list of medications that are, and are not, allowed in this study. Any changes in the list of allowed/not allowed medications will be communicated to investigators and will not constitute a protocol amendment. The concomitant use of acute medications to treat migraine is allowed, with some limitations. Treatments used for the prevention of migraine, including nutraceuticals and non-pharmacological interventions, are not allowed at any time during Treatment Phase and Follow-up Phase. Patients should have washed out all migraine preventive treatments at least 5 days prior to Visit 2. Botulinum toxin A or B in the head or neck area for therapeutic use is not allowed within 3 months prior to Visit 2. Nerve blocks or use of therapeutic devices (such as transcranial magnetic stimulation) in the head or neck area or for migraine prevention are not allowed within 30 days before Visit 2. Anti-CGRP antibodies (to either ligand or receptor) must be discontinued at least 5 half-lives prior to Visit 2.

Patients will capture whether they took any acute headache medication as part of their daily diary entry during Treatment Phase and Follow-up Phase. Acute headache medication name, dose, and date will be recorded by patients during Treatment Phase and Follow-up Phase on a headache medication log, which will be returned to site staff at each study visit.

Table [LAJB 7.1](#) Treatments Allowed and Treatments Not Allowed as Concomitant Therapy

A. Medications allowed for the ACUTE treatment of migraine headaches or other pain or injury:

Acetaminophen (paracetamol) up to 3000 mg/day, NSAIDs; Triptans; Ergotamine and derivatives; Isometheptene mukate, dichloralphenazone and acetaminophen combination (Midrin); or combinations thereof; ubrogepant;

The following medications are allowed with restrictions:

1. Opioid and barbiturates no more than 4 days/month.
2. Single dose of injectable steroids allowed only once during the study, in an emergency setting (SP II, III, IV).
3. Short term use of steroids, < 7days, for medical circumstances that may arise.

B. Medications, Procedures or Devices not allowed for any reason/indication in Study Period II (Baseline), III (Double-Blind Treatment), and IV (Follow-up):

ACE inhibitors

Acetazolamide

Acupuncture
 Anticonvulsants/Antiepileptics
 Antipsychotics
 Angiotensin receptor blockers (ARBs)
 Beta-blockers
 Botulinum toxin applied to head/neck area for therapeutic use

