**Table 5.1. Date and Timing Conventions**

Term	Definitions or Rule
Study Day	If assessment is on or after date of first treatment dose then (date of assessment) – (date of first study treatment dose) + 1 If assessment precedes first treatment dose then (date of assessment) – (date of first study treatment dose)
Baseline value	Baseline value is defined as the last reported assessment on or before the first dose (or discontinuation, if no treatment is given).
Screening period	Date of informed consent (Visit 1) through the day prior to Visit 2; includes all dates of study participation for those without Visit 2.
Baseline period	Visit 2 date through the day prior to study drug administration (for those receiving study drug); Visit 2 date through end of study participation for those who participating in Visit 2 but not receiving study drug.
Study treatment period	The 1-month double-blind treatment phase begins on the date of study drug administration (Visit 3) and continues through date of Month 1 visit (Visit 5) for those participating in Visit 5; continues through study withdrawal for those withdrawing prior to Visit 6 (Month 1.5). If patients do not attend Visit 5 but continue on study, the end of study treatment period will be the expected date of Visit 5 (i.e.30 days after Visit 3).

Follow-up period	Patients who continue on study after Visit 5 (or beyond expected date of Visit 5, if patient does not attend Visit 5 but attends later visits) will enter the follow-up period the day after the Visit 5 date (or expected date, where relevant), and continue for up to 140 days post-dose.
------------------	--

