## **5.6. Protocol Deviation**

Important protocol deviations are defined as deviations from the protocol that potentially could have a meaningful impact on study conduct or on the primary efficacy, safety, or pharmacokinetics (PK) outcomes for an individual participant. The criteria for identifying study important protocol deviations will be defined within the appropriate protocol-specific document and will be reviewed as part of the ongoing data cleaning process and data evaluation.

All important protocol deviations will be identified and documented prior to unblinding to confirm exclusion from the PPS. A summary and a listing of all important protocol deviation will be produced using the FAS.

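### Protocol Section 7.8 gives a 5-day preventive washout before Visit 2, where Section 5.1 and Exclusion 23 require 2 weeks

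*Protocol*

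**What the plan says.** Three places in the current protocol state the general washout for migraine preventives, all counted back from Visit 2.

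- Section 5.1 (Study Period I): "Patients are required to discontinue all excluded medications or treatments for migraine prevention at least 2 weeks prior to Visit 2".
- Section 6.2, Exclusion 23: "Patients must have discontinued such medications or treatments at least 2 weeks prior to Visit 2".
- Section 7.8: "Patients should have washed out all migraine preventive treatments at least 5 days prior to Visit 2".

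The opening of Section 6 adds: "Prospective approval of protocol deviations to recruitment and enrollment criteria, also known as protocol waivers or exemptions, are not permitted". The Schedule of Activities (Table LAJB 2.1) has a row for "Inclusion and exclusion criteria", marked at Visit 1, Visit 2 and Visit 3 predose. Its row "Allowable range (days) between visits" gives 3-90 for screening and 30-40 for baseline. SAP Table 5.1 defines the baseline period, for patients who are dosed, as "Visit 2 date through the day prior to study drug administration".

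**The concern.** Section 7.8 is where site staff look up medication rules, and it presents as sufficient an interval that makes a patient ineligible. A site that books Visit 2 from 7.8 could open the baseline diary less than 2 weeks after a preventive was stopped.

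The diary month that starts at Visit 2 carries much of the trial. It decides eligibility (Inclusion 4), the episodic or chronic stratum (Sections 5.2 and 7.2, Appendix 6), and both the change score and the baseline covariate in the primary model (Protocol 10.3.3.1, SAP 5.11.1). If a preventive is still acting, or its withdrawal is still being felt, the early diary days may not represent the patient's unmedicated state. The practical stake is a less reliable baseline for such patients, and for those near the 4-migraine-day or 15-headache-day threshold, a possible change in eligibility or stratum.

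**Working it through.** The documents give no figure to reproduce here. The check compares text and then does one short calculation.

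**Step 1. Compare Section 7.8 with Exclusion 23.**

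| Treatment | Exclusion 23 | Section 7.8 | Agree? |
|---|---|---|---|
| Migraine preventives in general | 2 weeks | 5 days | No |
| Botulinum toxin, head or neck | 3 months | 3 months | Yes |
| Nerve blocks and devices, head or neck | 30 days | 30 days | Yes |
| Anti-CGRP antibodies | 5 half-lives | 5 half-lives | Yes |

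Three of four intervals agree. That pattern suggests one wrong figure in a restatement of the same rule, not a separate rule.

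**Step 2. Which text governs?** The 2-week figure is an eligibility criterion, appears twice, and cannot be waived. It governs. A patient at 14 days or more meets every sentence; a patient at 5 to 13 days meets only 7.8.

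**Step 3. Could the schedule prevent this?** Screening may last 3 to 90 days. A gap of 5 to 13 days between stopping a preventive and Visit 2 fits inside that range, so the range does not by itself block it. A 14-day gap also fits, so the correct rule is workable.

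**Step 4. Baseline days inside the required washout.** Let d be the number of days from stopping the preventive to Visit 2, with 5 ≤ d ≤ 13 and the diary starting at Visit 2. Days inside the 14-day washout = 14 − d.

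- d = 5: 14 − 5 = 9 days.
- d = 13: 14 − 13 = 1 day.

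| Baseline length | 9 days inside | 1 day inside |
|---|---|---|
| 30 days | 9/30 = 30.0% | 1/30 = 3.3% |
| 40 days | 9/40 = 22.5% | 1/40 = 2.5% |

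The schedule's footnote a allows up to 5 more days to arrange Visit 3, although eligibility still rests on the 30- to 40-day period. Counted to the day before dosing, as SAP Table 5.1 does, the period could reach about 40 + 5 = 45 days, and the largest share would be 9/45 = 20%.

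These are shares of calendar days, not sizes of drug effect. The documents give no carry-over data, so no effect on counts or precision can be computed.

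**The case against.** **Stopping and clearing may be different events.** Exclusion 23 speaks of discontinuing and 7.8 of washing out, so one could read the pair as: stop by day −14, be clear of drug by day −5. The protocol never draws this distinction, and 7.8 sets the 5 days beside the same special-case limits as Exclusion 23. The reading is possible but not the natural one. What stands is a caution about the repair: changing only the number would leave a sentence that, on this reading, is stricter than Exclusion 23.

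**The rule is already controlled.** This largely stands. Criteria are checked at three visits, Section 6.4 allows rescreening with sponsor approval, and Section 8.1.2 covers inadvertent enrolment. A site that applies Exclusion 23 makes no error. Two limits remain. With a single infusion, discontinuing treatment under 8.1.2 achieves nothing once the dose is given. And the SAP's full analysis set keeps every randomised patient, so a missed case stays in the primary analysis.

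**The correction comes late.** SAP 5.11.2 and 5.11.4 report treatment-phase diary compliance and insufficient enrolment, so data already exist. This stands: for baselines already collected, the correction is documentary.

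**Stronger readings that the documents do not support.** A reader might infer that affected patients are put in the wrong stratum. Appendix 6 defines the stratum by counts recorded in the prospective baseline, so it is correct by definition; at most it may not reflect unmedicated frequency. A reader might infer a biased treatment comparison, but the washout error arises before randomisation and applies to both arms alike. A reader might add the steroid entries in Table 7.1, where List A item 3 permits short courses without naming a route and List B bars oral corticosteroids. That is a separate wording ambiguity with no shown effect, and nothing here depends on it.

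**Conclusion.** The inconsistency is real and is in current operative text. Section 7.8 states a shorter washout than the binding eligibility rule by 14 − 5 = 9 days. The exposure is confined to a patient whose preventive was stopped 5 to 13 days before Visit 2 and whose ineligibility was then missed at the scheduled checks. For that patient, 9 to 1 early diary days fall inside the required washout.

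This rests on reading the two sentences as the same rule and on the diary starting at Visit 2. How many patients are affected is not given and may be zero. No between-arm bias is expected, and any loss of precision cannot be computed from the documents. Severity: minor.

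**What to change.** Replace the Section 7.8 sentence with Exclusion 23's own wording, "Patients must have discontinued such medications or treatments at least 2 weeks prior to Visit 2", or with a cross-reference to that criterion. Using its verb as well as its interval avoids creating a third version of the rule.

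Make this as a correction to the protocol text. The clause in 7.8 that lets changes go out by communication to investigators covers the lists of allowed and disallowed medications, not this sentence. If it is handled as an amendment, Appendix 3.1.3 has it provided to the ethics boards. Sites should also be told that 2 weeks has been the rule throughout.

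For patients already in the study, a preventive stopped less than 14 days before Visit 2 is already a deviation from Exclusion 23 and should be recorded as such. Whether it counts as important is left by SAP 5.6 to another document: "The criteria for identifying study important protocol deviations will be defined within the appropriate protocol-specific document".

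The cost is one corrected sentence and the associated document handling. Eligibility, sample size and analysis do not change, and the 2-week interval fits the existing screening range.

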 Cannabis / Cannabinoids / Cannabidiol
 Chiropractic procedures, physiotherapy, TENS or other electric devices on head and neck
 Corticosteroids for oral use
 Flunarizine
 Gabapentin
 Herbals with anti-inflammatory effect (feverfew, willow bark, petasites/butterbur)
 Monoamine oxidase inhibitors (MAOIs)
 Memantine
 Methysergide
 Nerve block in head/neck area
 Oxetorone
 Pizotifen
 Pregabalin
 Serotonin 5HT2a/2c antagonists, eg, trazodone, nefazodone
 Stimulants (prescription strength), eg, methylphenidate, dextroamphetamine, mixed amphetamine salts
 Tizanidine
 Tricyclic antidepressants (TCAs)
 Triptans for prophylaxis of menstrual related migraine
 Venlafaxine
 Verapamil

C. Restricted medication during Study Period III (Double-Blind Treatment) and Study Period IV (Follow-up): Use of the following medications for indications other than migraine prevention is allowed providing the dose is stable 2 months prior to Visit 2 and is expected to remain stable during the Treatment Phase.

Benzodiazepines
 Bupropion
 Calcium-channel blockers (except verapamil, flunarizine, and lomerizine)
 Clonidine
 Guanfacine
 Mirtazapine
 SSRIs/NRIs/SNRIs (other than venlafaxine)
 Use of electric devices (ie, TENS), physiotherapy, chiropractic procedures on low back and extremities

D. Restricted medication during Study Period IV (Follow-up):

Medications from List B.
 Medications or treatments for migraine prevention.
 Medications in List C may now be started, stopped, or have dose modification as long as not being used for migraine prevention.

Abbreviations: 5HT = 5-hydroxytryptamine; ACE = angiotensin-converting enzyme; NRI = norepinephrine reuptake inhibitor; NSAID = nonsteroidal anti-inflammatory drug; SNRI = serotonin-norepinephrine reuptake inhibitor; SP = Study Period; SSRI = selective serotonin reuptake inhibitor; TENS = transcutaneous electrical nerve stimulation.

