Appendix 7. Protocol Amendment J1H-MC-LAJB(b) Summary

Overview

Protocol J1H-MC-LAJB, A Phase 2, Randomized, Double-Blind, Placebo-Controlled Study of LY3451838 in Adults with Treatment-Resistant Migraine, has been amended. The new protocol is indicated by amendment (b) and will be used to conduct the study in place of any preceding version of the protocol.

The overall changes and rationale for the changes made to this protocol are described in the following table. Other general editorial corrections and formatting changes not affecting content have been made in the document, and these changes are not identified in the amendment summary table or with strikethrough/underscore.

Amendment Summary for Protocol J1H-MC-LAJB Amendment (b)

Section # and Name	Description of Change	Brief Rationale
1. Synopsis	Number of patients updated.	Statistical calculations confirmed that CSF could be achieved with less patients
5.2 Number of Participants	Number of patients updated.	Statistical calculations confirmed that CSF could be achieved with less patients
6.1 Inclusion Criteria	Criterion 6 added 
 • Nortriptyline • Rimegepant and atogepant 	
 • For clarification. • Approved post protocol approval
7.8 Concomitant Therapy	Added short term use of steroids to Table 7.1.	To allow short term use of steroids
10.1 Sample Size Determination	
 • Number of patients updated • Sample size calculation assumptions updated 	Statistical calculations confirmed that CSF could be achieved with less patients
10.3.2.2 Patient Characteristics	Removed bullet, “Alcohol, tobacco, caffeine, and nicotine consumption”.	Said data is not being collected and thus, will not be statistically summarized
10.3.8 Interim Analysis	Replaced “all” with “majority of” patients to be included in the interim analysis.	To clarify what patients will be included

Revised Protocol Sections

Note:	Deletions have been identified by strike-throughs .
	Additions have been identified by the use of underline .

The numbering system used for inclusion and exclusion criteria provides a unique number for each criterion and allows for efficiency in data collection.

In case an amendment to the protocol adds a criterion, that criterion will receive the next available number, regardless of whether it is an inclusion or exclusion criterion.

1. Synopsis

Number of Patients:

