**Table 5.2. List of Analysis Sets**

Analysis Set	Definitions or Rule
Enrolled Patients	Includes all patients who have signed the informed consent
Screen Failures	Includes all patients who have signed the informed consent but are not treated or randomized
Full Analysis Set (FAS)	The FAS will include all patients who have been randomized to study treatment following the intent to treat (ITT) principle. Patients in this set will be grouped according to their allocated treatment. All patient characteristic and efficacy data will be presented using the FAS.
Per-protocol Set (PPS)	The PPS will include all patients who have been randomized to study treatment and did not have any major protocol deviations. Patients in this set will be grouped according to their allocated treatment. Additional efficacy analyses may be conducted on PPS.
Safety Analysis Set (SAF)	The SAF will include all patients who have been randomized to study treatment and have received at least 1 dose of study treatment (LY3451838 or placebo). Patients will be grouped according to actual treatment received.

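### Table LAJB 7.1 both allows and bars an oral corticosteroid course of under 7 days: List A item 3 and List B contradict each other and need reconciling

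*Protocol*

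**What the plan says.** All three rules stand in the current Table LAJB 7.1 of Protocol Section 7.8.

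- **List A, restricted items.** Under the line "The following medications are allowed with restrictions", item 2 reads "Single dose of injectable steroids allowed only once during the study, in an emergency setting (SP II, III, IV" and item 3 reads "Short term use of steroids, < 7days, for medical circumstances that may arise".
- **List B.** Its title is "Medications, Procedures or Devices not allowed for any reason/indication in Study Period II (Baseline), III (Double-Blind Treatment), and IV (Follow-up". One of its entries is "Corticosteroids for oral use".
- **List D.** For Study Period IV it names the List B medications again.

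The protocol's Appendix 7 records where item 3 came from: amendment (b) "Added short term use of steroids to Table 7.1". The reason given there is simply to permit such use.

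In the SAP, Section 5.10 refers to the same table for its list of concomitant medication. Table 5.2 defines a per-protocol set of randomized patients who "did not have any major protocol deviations". Section 5.6 leaves the criteria for important deviations to another protocol-specific document, and requires those deviations to be identified before unblinding.

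**The concern.** A site reading List A item 3 can conclude that a short oral steroid course for an intercurrent illness is acceptable. A site reading List B can conclude that it is not. Both would be following the current table.

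The stake is consistency. The same course may be given at one site and withheld at another. Where it is given, one site may report a deviation and another may not. The list of important deviations, and any analysis set built from it, would then depend partly on which list the site happened to apply. The affected periods include the prospective baseline and the treatment month, the two periods from which the primary endpoint is formed.

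**Working it through.** No arithmetic applies. The plan gives no figure for steroid use, and the point does not depend on power, effect size or sample size. The check compares the rules attribute by attribute, runs specific cases through them, and then looks for an exception.

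**Step 1. The rules side by side**

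| Attribute | List A item 2 | List A item 3 | List B entry |
|---|---|---|---|
| Status | Allowed, restricted | Allowed, restricted | Not allowed |
| Route | Injectable | Not stated | Oral |
| Duration or frequency | One dose, once in the study | Under 7 days; number of courses not stated | No limit stated |
| Circumstance | Emergency | Any medical circumstance | Any |
| Study periods | II, III, IV | Not stated | II, III, IV |

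**Step 2. Cases**

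| Case (Periods II to IV) | Item 2 | Item 3 | List B entry | Result |
|---|---|---|---|---|
| Oral, under 7 days, intercurrent illness | Does not apply | Allowed | Not allowed | **Contradiction** |
| Oral, 7 days or more | Does not apply | Outside its limit | Not allowed | One answer |
| First single injection in an emergency | Allowed | Allowed | Does not apply | One answer |
| Injections on several days, under 7 in total | Outside its limit | Allowed if read literally | Does not apply | Overlap, unclear |
| Other non-oral route, under 7 days | Does not apply | Allowed | Does not apply | One answer |

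Only the first case is a direct contradiction. The fourth is a weaker tension inside List A: item 2 sets a tight limit on injections, and item 3, which names no route, appears to relax it.

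**Step 3. Is there an exception anywhere?** List B has no carve-out for short courses, and its title excludes every reason, in its own words "not allowed for any reason/indication in Study Period II (Baseline), III (Double-Blind Treatment), and IV (Follow-up". Item 3 does not exclude the oral route. The text of Section 7.8 contains no cross-reference between the two entries. List D repeats the List B restriction for follow-up. The amendment summary states the purpose of item 3 but does not mention the List B entry. The SAP is silent on steroids.

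**Step 4. Which analyses could be touched?** SAP Section 5.1 and Table 5.2 put efficacy on the full analysis set, with patients grouped as randomized. Neither reading of Table LAJB 7.1 removes a patient from it. Table 5.2 makes efficacy analysis on the per-protocol set optional. The route to any result is therefore through deviation classification, and the criteria for that are in a document not supplied.

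**The case against.** The strongest reply is that the intent can be recovered. Item 3 is the later and narrower provision, added expressly to permit short steroid use, so a sensible site would read it as an exception to the general List B entry. Alternatively, item 3 could be confined to non-oral routes, and then nothing in List B conflicts with it. Section 7.8 also allows list changes to be sent to investigators outside an amendment, so a clarification may already exist.

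Part of this stands. Either reading would remove the contradiction, and the documents support saying that sites *may* differ, not that they will. But the two readings give opposite answers for an oral course, neither is written down, and List B's wording leaves no room for an implied exception. Whether a clarifying communication was sent cannot be seen from the documents.

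It can also be said that item 2 and item 3 address different situations, an emergency and a general medical need. That is fair, and it is why their overlap is treated here as secondary.

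A further reply is that important deviations are fixed before unblinding, so classification cannot be steered by treatment arm. That also stands. The problem is inconsistency between sites, not bias towards one arm.

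**Conclusion.** The contradiction is real, stands in the current text, and is limited to oral corticosteroid courses of under 7 days in Study Periods II to IV. A secondary overlap exists between List A items 2 and 3 for injectable courses of more than one dose.

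A reader might infer more than this, and the documents do not support it:

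- *That such a course is an important deviation that costs the patient a place in the per-protocol set.* The criteria are in a document not supplied, which may already deal with steroids.
- *That the primary result is compromised.* The primary analysis uses the full analysis set, so any effect is indirect.
- *That the harm can be sized by the share of endpoint days a course would cover.* That share would be the same for a non-oral course, where there is no contradiction, and it says nothing about the treatment contrast. The documents also give no expected frequency of steroid use.

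The size is therefore left unquantified. The conclusion rests on reading the table as written and on the absence of an exception in either document. It is worth correcting because two rules in force give opposite instructions and the correction costs little.

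**What to change.** The sponsor should reconcile List A items 2 and 3 with the List B oral corticosteroid entry, so that each combination of steroid route and duration has exactly one status in each of Study Periods II, III and IV. List D should be checked against the outcome. Which rule should stand is for the sponsor to decide, and nothing is proposed here.

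The deviation criteria in the protocol-specific document should then be aligned with the reconciled table, so that the same course is classified the same way at every site. If they already cover steroid use, this is only a consistency check.

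The cost is a few words in one table, a communication to sites, and a check of the deviation criteria. Section 7.8 states that changes to the medication lists do not count as a protocol amendment. No change to the statistical model or the sample size is involved.
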